7.9 Concomitant Medications and Other Anti-Cancer Treatments

Concomitant medication is defined as medication, other than protocol therapy, which is taken by patients any time on treatment or after end of treatment. Patients may also receive any other anti-cancer treatment during or after being taken off protocol treatment.

- Concomitant medications for patients during protocol treatment (reported on Chemotherapy Report, CRF Pre-Excision Report, and CRF Surgery Report) (**Table 46**)
- Concomitant medications for patients 30 days after excision (reported on CRF Follow-Up Report) (**Table 46**)
- Anti-cancer treatments for patients during protocol treatment (reported on Chemotherapy Report, CRF Pre-Excision Report, and CRF Surgery Report) (**Table 47**)
- Anti-cancer treatments for patients after protocol treatment but before relapse (reported on Follow-Up Report) (**Table 47**)
- Anti-cancer treatments for patients after relapse (reported on Short Follow-Up Report) (**Table 47**)

7.10 Quality of Life

The quality of life of patients in this study is assessed by using EORTC QLQ-C30 (version 3.0), QLQ-CR29, Low Anterior Resection Syndrome Score (LARS), and the Fecal Incontinence Quality of Life (FIQL) Instrument at baseline, pre-excision (2 weeks (FOLFOX) or 3 weeks (CAPOX) after last injection in last cycle of chemotherapy), after excision (months 6, 12, 24, and 36). The following are the scoring algorithms for each of these four QoL instruments.

7.10.1 Scoring Algorithms

7.10.1.1 EORTC QLQ-C30

The EORTC core questionnaire, QLQ-C30 (version 3.0), consists of five Functional Scales, Global Health Status, and nine Symptoms Scales. Each scale in the questionnaire will be scored (0 to 100) according to the EORTC recommendations in the EORTC QLQ-C30 Scoring Manual. The scoring method for EORTC QLQ-C30 is summarized below. In this summary Qi refers to the i-th question on the QLQ-C30.

Functional scale's scores:

- Physical functioning: $(1 - ((Q1+Q2+Q3+Q4+Q5)/5 - 1)/3) * 100$
- Role functioning: $(1 - ((Q6+Q7)/2-1)/3) * 100$
- Emotional functioning: $(1 - ((Q21+Q22+Q23+Q24)/4-1)/3) * 100$
- Cognitive functioning: $(1 - ((Q20+Q25)/2-1)/3) * 100$
- Social functioning: $(1 - ((Q26+Q27)/2-1)/3) * 100$

Global health status score:

- Global QOL: $((Q29+Q30)/2-1)/6 * 100$

Symptom scale's scores:

- Fatigue: $((Q10+Q12+Q18)/3-1)/3 * 100$
- Nausea and vomiting: $((Q14+Q15)/2-1)/3 * 100$
- Pain: $((Q9+Q19)/2-1)/3 * 100$
- Dyspnea: $((Q8-1)/3 * 100$
- Insomnia: $(Q11-1)/3 * 100$
- Appetite loss: $(Q13-1)/3 * 100$
- Constipation: $(Q16-1)/3 * 100$
- Diarrhea: $(Q17-1)/3 * 100$
- Financial difficulties: $(Q28-1)/3 * 100$

7.10.1.2 EORTC QLQ-CR29

QLQ-CR29 is a colon and rectum cancer site-specific supplemental module to the EORTC core questionnaire, which consists of five Functional Scales, 18 Symptoms Scales as well as stoma status. Each scale in the questionnaire will be scored (0 to 100) according to the EORTC recommendations in the EORTC QLQ-CR29 Scoring Manual. The scoring method for EORTC QLQ-CR29 is summarized below. In this summary Qi refers to the i-th question on the QLQ-CR29.

Functional scale's scores:

- Body image: $(1 - ((Q45+Q46+Q47)/3 - 1)/3) * 100$
- Anxiety: $(1 - (Q43-1)/3) * 100$
- Weight: $(1 - (Q44-1)/3) * 100$
- Sexual Interest (men): $(1 - (Q56-1)/3) * 100$
- Sexual Interest (women): $(1 - (Q58-1)/3) * 100$

Symptom scale's scores:

- Urinary frequency $((Q31+Q32)/2-1)/3 * 100$
- Blood and mucus in stool $((Q38+Q39)/2-1)/3 * 100$
- Stool frequency $((Q52+Q53)/2-1)/3 * 100$
- Urinary incontinence $(Q33-1)/3 * 100$
- Dysuria $(Q34-1)/3 * 100$
- Abdominal pain $(Q35-1)/3 * 100$
- Buttock pain $(Q36-1)/3 * 100$
- Bloating $(Q37-1)/3 * 100$
- Dry mouth $(Q40-1)/3 * 100$
- Hair loss $(Q41-1)/3 * 100$
- Taste $(Q42-1)/3 * 100$
- Flatulence $(Q49-1)/3 * 100$
- Fecal incontinence $(Q50-1)/3 * 100$
- Sore skin $(Q50-1)/3 * 100$
- Embarrassment $(Q54-1)/3 * 100$
- Stoma care problems $(Q55-1)/3 * 100$
- Impotence $(Q57-1)/3 * 100$
- Dyspareunia $(Q59-1)/3 * 100$
- Stoma status $(Q48-1) * 100$

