The EORTC QLQ-CR29 subscale supplements the core questionnaire with 29 items specific for patients with colorectal cancer. There are 18 items that deal with gastrointestinal symptoms, separate items for those with stomas and four sexual function items. These items comprise 6 scales and 11 individual items [*Gujral 2007; Whistance 2009*]. The EORTC core and subscale have been validated in various patient groups and translated into several languages.

Two rectal cancer specific functional scales will be used by this trial, the Fecal Incontinence Quality of Life (FIQL) and the Low Anterior Resection Syndrome (LARS) instruments [*Rockwood 2000; Juul 2014*]. These instruments have been developed to follow patients undergoing standard rectal surgery (i.e. TME) and have been previously reported for patients undergoing organ sparing transanal procedures [*Planting 2013*].

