25. Have you had difficulty remembering things?	1	2	3	4
26. Has your physical condition or medical treatment interfered with your family life?	1	2	3	4
27. Has your physical condition or medical treatment interfered with your social activities?	1	2	3	4
28. Has your physical condition or medical treatment caused you financial difficulties?	1	2	3	4

For the following questions please circle the number between 1 and 7 that best applies to you.

29. How would you rate your overall health during the past week?	1 Very Poor	2	3	4	5	6	7 Excellent
30. How would you rate your overall quality of life during the past week?	1 Very Poor	2	3	4	5	6	7 Excellent

Patients sometimes report that they have the following symptoms. Please indicate the extent to which you have experienced these symptoms during the past week.

During the past week:	Not At All	A Little	Quite a Bit	Very Much
31. Did you urinate frequently during the day?	1	2	3	4
32. Did you urinate frequently during the night?	1	2	3	4
33. Have you had any unintentional release (leakage) of urine?	1	2	3	4
34. Did you have pain when you urinated?	1	2	3	4
35. Did you have abdominal pain?	1	2	3	4
36. Did you have pain in your buttocks/anal area/rectum?	1	2	3	4
37. Did you have a bloated feeling in your abdomen?	1	2	3	4
38. Have you had blood in your stools?	1	2	3	4
39. Have you had mucus in your stools?	1	2	3	4
40. Did you have a dry mouth?	1	2	3	4
41. Have you lost hair as a result of your treatment?	1	2	3	4
42. Have you had problems with your sense of taste?	1	2	3	4
43. Were you worried about your health in the future?	1	2	3	4
44. Have you worried about your weight?	1	2	3	4
45. Have you felt physically less attractive as a result of your disease or treatment?	1	2	3	4
46. Have you been feeling less feminine/masculine as a result of your disease or treatment?	1	2	3	4
47. Have you been dissatisfied with your body?	1	2	3	4

48. Do you have a stoma bag (colostomy/ileostomy)?
(please circle the correct answer)

Yes

No

During the past week:

Not
At All A
Little Quite
a Bit Very
Much

Answer these questions ONLY IF YOU HAVE A STOMA BAG, if not please continue below:

49. Have you had unintentional release of gas/flatulence from your stoma bag?

1 2 3 4

50. Have you had leakage of stools from your stoma bag?

1 2 3 4

51. Have you had sore skin around your stoma?

1 2 3 4

52. Did frequent bag changes occur during the day?

1 2 3 4

53. Did frequent bag changes occur during the night?

1 2 3 4

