54. Did you feel embarrassed because of your stoma?

1 2 3 4

55. Did you have problems caring for your stoma?

1 2 3 4

Answer these questions ONLY IF YOU DO NOT HAVE A STOMA BAG:

49. Have you had unintentional release of gas/flatulence from your back passage?

1 2 3 4

50. Have you had leakage of stools from your back passage?

1 2 3 4

51. Have you had sore skin around your anal area?

1 2 3 4

52. Did frequent bowel movements occur during the day?

1 2 3 4

53. Did frequent bowel movements occur during the night?

1 2 3 4

54. Did you feel embarrassed because of your bowel movement?

1 2 3 4

During the past 4 weeks:

Not
At All A
Little Quite
a Bit Very
Much

For MEN only:

56. To what extent were you interested in sex? 1 2 3 4

57. Did you have difficulty getting or maintaining an
erection? 1 2 3 4

For WOMEN only:

58. To what extent were you interested in sex? 1 2 3 4

59. Did you have pain or discomfort during intercourse? 1 2 3 4

Fecal Incontinence Quality of Life Instrument

Q 1: In general, would you say your health is:

- 1 Excellent
- 2 Very Good
- 3 Good
- 4 Fair
- 5 Poor

Q 2: For each of the items, please indicate how much of the time the issue is a concern for you due to accidental bowel leakage.

Q2. Due to accidental bowel leakage:	Most of the Time	Some of The Time	A Little of the Time	None of the Time
	1	2	3	4
a. I am afraid to go out.				
b. I avoid visiting friends.	1	2	3	4
c. I avoid staying overnight away from home.	1	2	3	4
d. It is difficult for me to get out and do things like going to a movie or to church.	1	2	3	4
e. I cut down on how much I eat before I go out.	1	2	3	4
f. Whenever I am away from home, I try to stay near a restroom as much as possible.	1	2	3	4
g. It is important to plan my schedule (daily activities) around my bowel pattern.	1	2	3	4
h. I avoid traveling.	1	2	3	4
i. I worry about not being able to get to the toilet in time.	1	2	3	4
j. I feel I have no control over my bowels.	1	2	3	4
k. I can't hold my bowel movement long enough to get to the bathroom.	1	2	3	4
l. I leak stool without even knowing it.	1	2	3	4
m. I try to prevent bowel accidents by staying very near a bathroom.	1	2	3	4

Q 3: Due to accidental bowel leakage, indicate the extent to which you AGREE or DISAGREE with each of the following items.

Q3. Due to accidental bowel leakage:	Strongly Agree	Somewhat Agree	Somewhat Disagree	Strongly Disagree
a. I feel ashamed.	1	2	3	4
b. I can not do many of things I want to do.	1	2	3	4

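### SAP 7.10.1.2 scores the CR29 sore-skin scale from item 50 (stool leakage), so item 51 is never used and sore skin duplicates fecal incontinence

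*SAP*

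**What the plan says.** SAP 7.10.1.2 states that the CR29 has five functional scales, 18 symptom scales and a stoma-status item. It says that scoring follows the EORTC manual for the module and then prints a formula for each scale, where Qi is the i-th question. Two single-item symptom scales have the same right-hand side: "Fecal incontinence $(Q50-1)/3 * 100" and "Sore skin $(Q50-1)/3 * 100".

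The questionnaire in Protocol Appendix V prints items 49 to 54 in two versions under the same numbers.

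| Item | Version for patients with a stoma | Version for patients without a stoma |
|---|---|---|
| 50 | "Have you had leakage of stools from your stoma bag" | "Have you had leakage of stools from your back passage" |
| 51 | "Have you had sore skin around your stoma" | "Have you had sore skin around your anal area" |

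The second version is headed "Answer these questions ONLY IF YOU DO NOT HAVE A STOMA BAG".

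Under SAP 7.10.4.1 and 7.10.4.2, every CR29 scale goes into the baseline summary (Table 49), the change scores (Table 50) and the deteriorated, improved or stable proportions (Table 51).

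**The concern.** A scale labelled sore skin is computed from the stool-leakage question. The sore-skin answers are collected but enter no formula. A program that follows the SAP literally would report the fecal-incontinence results a second time under the sore-skin label.

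Quality of life in all patients is a secondary objective, and the protocol's rationale stresses bowel function and incontinence as harms of radical surgery. Peri-anal or peri-stomal skin soreness is a separate complaint from leakage. As written, the trial would have no result for it, and a reader of the tables could take two matching rows as two findings.

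**Working it through.** No sample size, power or alpha is involved. The check is whether the printed formulas map onto the printed items.

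**1. Numbering.** The SAP formulas use the numbers of the Appendix V form. For example, urinary frequency uses 31 and 32, body image 45 to 47, and stoma status 48, which are the items on those subjects. Q50 in the SAP is therefore item 50 on the form.

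**2. Reproducing the SAP's scale count.**

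- Functional scales: body image (45, 46, 47), anxiety (43), weight (44), sexual interest in men (56) and in women (58). That is 5 scales and 3 + 1 + 1 + 1 + 1 = 7 item uses.
- Two-item symptom scales: urinary frequency (31, 32), blood and mucus in stool (38, 39), stool frequency (52, 53). That is 3 scales and 6 item uses.
- Single-item symptom scales: 33, 34, 35, 36, 37, 40, 41, 42, 49, 50 (fecal incontinence), 50 (sore skin), 54, 55, 57, 59. That is 15 scales and 15 item uses.
- Stoma status: 48, 1 item use.

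The symptom scales number 3 + 15 = 18, so the stated counts of 5 and 18 reproduce.

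**3. Item coverage.** Items 31 to 59 are 59 − 31 + 1 = 29 items. The formulas make 7 + 6 + 15 + 1 = 29 item uses but reach only 28 different items, because item 50 appears twice. The one item missing is 51. If sore skin uses item 51, the 29 uses cover the 29 items once each.

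**4. Size for one patient.** The score is (Q − 1)/3 × 100, so one answer category is worth 1/3 × 100 = 33.3 points.

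| Q50 | Q51 | Sore skin as printed, from Q50 | Sore skin from Q51 | Printed minus correct |
|---|---|---|---|---|
| 1 | 4 | 0 | 100 | −100 |
| 4 | 1 | 100 | 0 | +100 |
| 2 | 3 | 33.3 | 66.7 | −33.3 |
| 1 | 2 | 0 | 33.3 | −33.3 |

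**5. Consequence in the tables.** The two formulas are the same function of the same item. N, mean and standard deviation in Tables 49 and 50, and the proportions in Table 51, would therefore agree exactly for the two scales. A patient who answered item 51 but left item 50 blank would count as missing for sore skin.

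**The case against.** The best defence is that this is a one-character slip. The SAP names the EORTC manual as its authority and presents the list as a summary of it, and every other item from 31 to 59 appears once. A programmer working from the manual might never produce the error, and two identical rows could be noticed when the tables are checked. This is a fair account of how the slip arose and of how it might be caught. It does not make the printed rule right. The formula is what code will be written or validated against, and in the form in Appendix V item 50 is not about skin in either version.

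A reader might go further and infer that the SAP is also wrong to put the stoma and no-stoma wordings of items 49 to 54 into one score. Protocol 2.0 itself describes the module as having "separate items for those with stomas and four sexual function items". SAP 7.10.4 and Tables 50 and 51 have no split by item 48, so for a patient who gains a stoma the change score sets a bag answer against an anal answer. The observation is accurate, but the documents do not show an error:

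- The form gives both versions the same item numbers, so one formula per number may be what the instrument intends. The scoring manual that would settle this is not among the documents.
- The objective is quality of life in all patients. Limiting change scores to those without a stoma at both visits would select on an outcome of treatment.
- Stoma status is scored as its own CR29 item, and the footnote to Table 50 covers every CR29 item. The shift in stoma use would therefore be visible beside the bowel scales, though it would not separate them.

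Nor can the size of such an effect be worked out. The documents give no stoma share for this trial. The complements of the 50% and 65% design rates do not give the TME share of all 58 patients, because the primary denominator in SAP 7.7.1 is patients who had chemotherapy and TEMS or TAMIS. The 25% non-sphincter-sparing rate in Protocol 2.0 comes from stage II/III trials and does not count temporary stomas.

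**Conclusion.** The sore-skin formula is wrong as printed. Item 50 is used twice, item 51 is unused, and 2 of 18 symptom scales would be identical for every patient and visit. Individual sore-skin scores could be off by up to 100 points in either direction. The effect on group means depends on how far answers to items 50 and 51 differ, which the documents cannot tell us. The conclusion rests only on the formulas in SAP 7.10.1.2 and the form in Protocol Appendix V, and it assumes that the analysis follows those formulas.

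The point is minor. It affects descriptive secondary quality-of-life output in Tables 49 to 51. The primary endpoint, the two-stage decision rule and the relapse and survival estimates are untouched. The absence of a split by stoma status is a reporting choice that could be improved; its effect is unknown.

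**What to change.** In SAP 7.10.1.2, change the sore-skin formula to (Q51-1)/3 × 100, and check that any analysis program already written uses item 51. The cost is one digit and a short code check. No new data are needed.

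Optional: at months 6, 12, 24 and 36, show flatulence, fecal incontinence, sore skin, stool frequency and embarrassment also by stoma status, using the raw yes/no answer to item 48 and giving N. Keep the all-patient results as planned. The cost is a sentence in SAP 7.10.4 and extra rows for 5 scales × 4 visits = 20 scale-by-visit combinations in each table where the split is shown. Each combination carries several statistics per group. The stoma group may be very small, and the two groups are formed after treatment, so the split is for description only. If it is added to Table 51, the direction of improvement should be reversed for these symptom scales, as Protocol 13.6 requires.

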7.10.1.3 Low Anterior Resection Syndrome (LARS) Score

Low Anterior Resection Syndrome (LARS) Score is a scoring system for bowel dysfunction after low anterior resection (LAR) for rectal cancer. It consists of 5 questions and the answers to them are assigned a score based on the following algorithm:

Question 1: Do you ever have occasions when you cannot control your flatus (wind)?

- No, never 0
- Yes, less than once per week 4
- Yes, at least once per week 7

Question 2: Do you ever have any accidental leakage of liquid stool?

- No, never 0
- Yes, less than once per week 3
- Yes, at least once per week 3

Question 3: How often do you open your bowels?

- More than 7 times per day (24 hours) 4
- 4-7 times per day (24 hours) 2
- 1-3 times per day (24 hours) 0
- Less than once per day (24 hours) 5

Question 4: Do you ever have to open your bowels again within one hour of the last bowel opening?

- No, never 0
- Yes, less than once per week 9
- Yes, at least once per week 11

Question 5: Do you ever have such a strong urge to open your bowels that you have to rush to the toilet?

- No, never 0
- Yes, less than once per week 11
- Yes, at least once per week 16

LARS total score is defined as the sum of scores to these 5 questions.

7.10.1.4 Fecal Incontinence Quality of Life (FIQL) Instrument

The Fecal Incontinence Quality Of Life (FIQL) Instrument is a disease-specific tool designed to evaluate the impact of Fecal Incontinence (FI). It consists of four scales. Each scale in the instrument will be scored (1 to 4), where 1 is very affected and 4 is not affected, based on the scoring method summarized below. In this summary, Q_i refers to the i -th question on the FIQL instrument:

FIQL scale's scores:

- Lifestyle: $(Q2A+Q2B+Q2C+Q2D+Q2E+Q2G+Q2H+Q3B+Q3L+Q3M)/10$
- Coping/Behavior: $(Q2F+Q2I+Q2J+Q2K+Q2M+Q3C+Q3H+Q3J+Q3N)/9$
- Depression/Self Perception: $(Q1+Q3D+Q3F+Q3G+Q3I+Q3K+Q4)/7$
(Question 1 is reverse coded first)

- Embarrassment: $(Q2L+Q3A+Q3E)/3$

For all of questionnaires/instruments, missing items in a scale will be handled by the following methods: Values will be imputed for missing items by “assuming that the missing items have values equal to the average of those items which are present” for any scale in which at least half the items are completed. A scale in which less than half of the items are completed will be treated as missing.

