7.10.4.3 Proportions of LARS Severity Group at Baseline and Post-baseline Assessment

Based on the LARS total score of LARS, a patient can be classified into one of the following 4 groups: 0 to 20 (no LARS), 21 to 29 (minor LARS), and 30 to 42 (major LARS). Proportions of patients in each of these four groups and associated 95% confidence interval will be calculated at baseline and each time of post-baseline assessments (**Table 52**).

8. Appendices

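### The SAP's missing-item rule, applied to LARS as written, can give totals above 42 and severity groups that no answer could produce

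*SAP*

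**What the plan says.** The rule stands at the end of SAP 7.10.1.4, after the FIQL scoring, but its scope is general: "For all of questionnaires/instruments, missing items in a scale will be handled by the following methods". Missing items are filled by "assuming that the missing items have values equal to the average of those items which are present", and this is done "for any scale in which at least half the items are completed". LARS has five items, so three or more answers are enough and one or two items may be imputed. Neither document exempts LARS or gives it another rule.

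SAP 7.10.1.3 gives each LARS answer its own score and adds the scores: "LARS total score is defined as the sum of scores to these 5 questions". The top scores differ widely between items. For flatus (Q1) the top answer is "Yes, at least once per week 7", for liquid stool (Q2) it is "Yes, at least once per week 3", and for bowel frequency (Q3) it is "Less than once per day (24 hours) 5". Clustering (Q4) reaches 11 and urgency (Q5) reaches 16.

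SAP 7.10.4.3 classifies the total as "0 to 20 (no LARS), 21 to 29 (minor LARS), and 30 to 42 (major LARS"). No group is defined above 42. The total feeds the baseline mean (Table 49), the change scores (Table 50) and the severity proportions with 95% confidence intervals (Table 52).

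**The concern.** Filling a gap with the mean of the answered items is sound when a scale is an average of items on a common range, as in the EORTC multi-item scales. There it amounts to averaging the answers given. LARS is a sum, and its scores carry the weighting. The mean of the other four items says little about an item that can score at most 3, or about one that can score 16. The rule therefore tends to overstate the total when a low-weight item is missing and to understate it when Q5 is missing.

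At stake are the LARS means, change scores and severity proportions. Quality of life in all patients is a secondary objective, and the protocol background expects better function from organ-sparing treatment. With 58 patients accrued, one reclassified patient moves a severity proportion by 1/58 = 1.7 percentage points at a visit where all forms are in, and by more where fewer are.

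**Working it through.** **Inputs (SAP 7.10.1.3).** Item scores: Q1 0/4/7; Q2 0/3/3; Q3 4/2/0/5; Q4 0/9/11; Q5 0/11/16.

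**The plan's own range.** 7 + 3 + 5 + 11 + 16 = 42 and the minimum is 0. This reproduces the 0 to 42 implied by SAP 7.10.4.3.

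**The rule as a formula.** Let S be the sum of the answered items.

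- One item missing: total = S + S/4 = S × 5/4.
- Two items missing: total = S + 2 × S/3 = S × 5/3.

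The multiplier does not depend on which item is missing.

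**A total outside the scale.** Q2 missing, the others at maximum: S = 7 + 5 + 11 + 16 = 39. The imputed item is 39/4 = 9.75, against an item maximum of 3. The total is 39 + 9.75 = 48.75. With Q2 and Q3 missing, S = 7 + 11 + 16 = 34 and the total is 34 × 5/3 = 56.67.

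**A group no answer could produce.** Q2 missing, Q1 = 0, Q3 = 0, Q4 = 9, Q5 = 16: S = 25. The true total can only be 25 or 28, both minor LARS. The rule gives 25 × 5/4 = 31.25, major LARS.

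**The opposite direction.** Q5 missing, Q1 to Q4 = 4, 3, 2, 9: S = 18 and the rule gives 22.5, minor LARS. The true total is 18 (no LARS), 29 (minor) or 34 (major), depending on urgency. The imputed group is right for one of these three and wrong for two.

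**Enumeration.** There are 3 × 3 × 4 × 3 × 3 = 324 answer patterns. Removing each item in turn gives 324 × 5 = 1620 cases, counted equally. For the wrong-group column, a total above 42 is read as major LARS.

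| Item missing | Largest total | Totals above 42 | Wrong group, of 324 |
|---|---|---|---|
| Q1 | 43.75 | 12 | 73 |
| Q2 | 48.75 | 33 | 71 |
| Q3 | 46.25 | 28 | 55 |
| Q4 | 38.75 | 0 | 130 |
| Q5 | 32.5 | 0 | 193 |
| All | 48.75 | 73 of 1620 (4.5%) | 522 of 1620 (32%) |

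All 73 cases above 42 are truly major LARS. Of the 522 wrong groups, 279 are too mild and 243 too severe. All 71 errors with Q2 missing are upward; 162 of the 193 with Q5 missing are downward.

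**How much of this is the rule's doing.** Any method must guess the missing answer. Take as benchmark the rule that assigns, for each set of four answers, the group that most of the possible fifth answers would give. It is wrong in 365 of 1620 cases (22.5%), and in 135 of 324 (42%) when Q5 is missing. The excess from the SAP rule is 522 − 365 = 157 of 1620 (9.7%) overall, and 193 − 135 = 58 of 324 (18%) for Q5.

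**Plainly impossible groups.** There are 4 × 108 + 81 = 513 distinct sets of four observed answers. In 27 of them (5.3%) the rule assigns a group that no answer to the missing item could give.

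**The case against.** The strongest reply concerns size. Adding the 73 totals above 42 to the 522 wrong groups gives 595 of 1620 (37%), and for a missing Q5 the figure is 193 of 324 (60%). A reader might infer that the rule itself misclassifies that share of incomplete forms. The documents do not support this. All 73 are truly major LARS, so a program that codes 30 or more as major classifies them correctly. Much of the rest is unavoidable, as the 22.5% and 42% benchmarks show. Equal weighting of answer patterns is also an assumption: it shows the mechanism and does not predict this trial's rate.

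A reader might also infer that Table 52 will be materially wrong. The documents give no rate of missing LARS items. Protocol Appendix V has the research associate check each questionnaire and prompt for overlooked questions, the cover page records whether everything was answered, and the form asks the patient to check. LARS is five tick-box items, one of four quality-of-life instruments, and is summarised descriptively. No test or stopping decision uses it.

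All of this stands, and it limits the impact. It does not rescue the rule. A cap at 42 would leave the 522 wrong groups in place, and a total of 31.25 where only 25 or 28 is possible is wrong however rarely it occurs.

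**Conclusion.** The rule is wrong as written for LARS. Followed literally, it can give totals up to 48.75 with one item missing and can assign groups that the observed answers exclude. Under equal weighting of single-missing patterns, it picks a wrong group in 32% of cases against 22.5% for the best single-group guess, and with Q5 missing in 60% against 42%. These figures apply only to forms with exactly one LARS item missing, and how many such forms there are is unknown and may be few. The consequence is confined to the descriptive LARS results in Tables 49, 50 and 52. The organ preservation analysis is unaffected. The point is worth correcting because the error is certain in kind and the remedy is short, not because a large distortion has been shown.

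**What to change.** Add one sentence to the missing-item paragraph of SAP 7.10.1.4 that exempts LARS from the half-items rule. If any of the five LARS items is missing, the LARS total is set to missing. The severity group is set to missing too or, as an alternative, is assigned only when every possible answer to the missing item leads to the same group. In the Q2 example above, 25 and 28 are both minor LARS, so that alternative would keep the patient in Table 52. Report the number of LARS forms with a missing total at each visit.

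Leave the rule unchanged for the EORTC scales. This point proposes no change for FIQL.

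The cost is the sentence and the loss of a few LARS scores. If incomplete forms are rare, little is lost; if they are common, the reported count will show it.
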